### Important Instructions for Using This Protocol Template:

1. Add this completed protocol template to your study in CATS IRB (<http://irb.psu.edu>) on the "Basic Information" page, item 7.
2. This template is provided to help investigators prepare a protocol that includes the necessary information needed by the IRB to determine whether a study meets all applicable criteria for approval.
3. Type your protocol responses below the gray instructional boxes of guidance language. If the section or item is not applicable, indicate not applicable.
4. For research being conducted at Penn State Hershey or by Penn State Hershey researchers only, delete the instructional boxes from the final version of the protocol prior to upload to CATS IRB (<http://irb.psu.edu>). For all other research, do not delete the instructional boxes from the final version of the protocol.
5. When making revisions to this protocol as requested by the IRB, please follow the instructions outlined in the Study Submission Guide available in the Help Center in CATS IRB (<http://irb.psu.edu>) for using track changes.

### If you need help...

## 1.0 Objectives

### 1.1 Study Objectives

Describe the purpose, specific aims or objectives. State the hypotheses to be tested.

The purpose of the study is to evaluate the effects of nighttime peanut consumption (i.e., after dinner and before sleep) on fasting blood glucose levels, longer-term blood glucose control, and risk factors for cardiovascular disease. Furthermore, this study will investigate the relationship between the microbiota, shifts in the microbiota with peanut consumption and the effect on blood glucose regulation. There is some emerging evidence that the microbiome predicts glycemic response and this study would provide the first robust test of the role of the microbiome in blood glucose regulation in response to peanut consumption.

The aims of the study are as follows:

- To determine the effect of consuming one ounce of peanuts as an evening snack (after dinner and before sleep) on glycemic control and risk factors for cardiovascular disease, compared with an isocaloric high carbohydrate snack, in people with impaired fasting glucose.
- To assess changes in the profile of the gut bacterial community in response to the peanut treatment, compared with an isocaloric high carbohydrate snack, in people with impaired fasting glucose.
- To investigate the relationship between markers of glycemic control, after each treatment, and shifts in the microbiota to elucidate the role of the microbiome in glucose regulation.

#### Hypothesis

- consuming peanuts as an evening snack will reduce fasting glucose levels compared to an isocaloric high carbohydrate control snack.
- Improvements in fasting glucose levels with peanut consumption will be correlated with favorable shifts in the microbiota i.e. peanut consumption will result in enrichment of bacteria known to be biomarkers of a healthy gut and these shifts will be associated with the magnitude of blood glucose lowering observed.

### 1.2 Primary Study Endpoints

State the primary endpoints to be measured in the study. Clinical trials typically have a primary objective or endpoint. Additional objectives and endpoints are secondary. The endpoints (or outcomes), determined for each study subject, are the quantitative measurements required by the objectives. Measuring the selected endpoints is the goal of a trial (examples: response rate and survival).

Fasting plasma glucose

### 1.3 Secondary Study Endpoints

State the secondary endpoints to be measured in the study.

- Fructosamine
- Fasting insulin
- Microbiome
- Peripheral and central blood pressure
- Augmentation index
- Pulse wave velocity
- Lipids/lipoproteins
- Weight
- Dietary intake (calorie, macronutrient and overall diet quality).

## 2.0 Background

### 2.1 Scientific Background and Gaps

Describe the scientific background and gaps in current knowledge.

Approximately 34% of adults in the U.S. have pre-diabetes, defined as impaired fasting glucose or impaired glucose tolerance, placing them at substantially higher risk of developing type 2 diabetes. Seventy-five percent of middle-aged people with pre-diabetes will develop type 2 diabetes in their lifetime. In addition, individuals with pre-diabetes also present with a greater number of cardiovascular risk factors and have a 10-20% higher risk of cardiovascular disease. Therefore, it is a **public health priority** to identify strategies to reduce fasting blood glucose in individuals with pre-diabetes to delay the onset of type 2 diabetes.

A number of observational studies show nut consumption reduces diabetes risk. A pooled analysis of five prospective cohort studies and one randomized controlled trial showed a 13% reduction in type 2 diabetes risk with consumption of 4 servings (28.4 g/serving) of nuts per week. A more recent systematic review and meta-analysis of four studies showed that per 28 g/day of peanuts and tree nuts, risk of diabetes mortality was reduced by 39%. There is convincing evidence from observational research to show that nuts, including peanuts reduce diabetes risk, and this is likely mediated by improvements in blood glucose control.

The effect of consuming peanuts as an evening snack on fasting glucose levels has not been tested. This is despite the clinical observations that fasting blood glucose is lower when nuts or nut butters are consumed in the evening. Adding support to these clinical observations is a study showing that a pre-bedtime snack of uncooked corn starch (Extend bar), a slow digesting, complex carbohydrate prevented overnight blood glucose excursions and reduced fasting blood glucose levels in adults with type 2 diabetes.

These observations may be explained in part by a blunting of the Dawn Phenomenon. The Dawn Phenomenon is characterized by a rise in early morning fasting blood glucose. At present it is thought that the Dawn Phenomenon is caused by excessive glucose production by the liver “at dawn”, in the absence of insulin, and thus elevations in fasting blood glucose are observed. Identifying successful strategies to counteract this physiological effect is of importance because a rise in fasting blood glucose levels of more than 50 mg/dL can result in daylong hyperglycemia. Furthermore, the Dawn Phenomenon is not effectively treated by the current oral hypoglycemic agents and therefore an opportunity exists to identify an effective strategy to blunt the Dawn Phenomenon, a substantial cause of poor glycemic control, and improve overall glycemic control.

Emerging evidence suggests that the microbiome may determine glycemic response. Large individual variation has been observed in glycemic response to foods differing in glycemic index, and this has largely been poorly understood. However, recently, a one-week randomized controlled trial of two different bread treatments showed that the glycemic response to the bread type could be predicted based on the microbiome. This paper, published in Cell Metabolism (impact factor 18.16), provides some of the first evidence that the microbiome may mediate glycemic response. Although this study was only one week long so changes in the microbiome could not be detected. Therefore, we propose to conduct a 6 week study to allow investigation of: 1) the effect of the microbiome on glycemic response to peanuts vs. the control snack; and 2) how changes in the microbiome in response to peanut consumption correlate with changes in glucose regulation.

Recent data suggests that tree nut consumption for between three and six weeks changes the microbiome; no studies have assessed the effect of peanuts on the microbiome. In many of these studies there were changes in the relative abundance of microbiota known to be associated with beneficial health effects.

### 2.2 Previous Data

Describe any relevant preliminary data.

Previous meal studies from our lab and others have demonstrated that consumption of peanuts with a meal reduces post-meal blood glucose levels. In a study led by [name], blood glucose levels were lower 4 hours after consumption of a high-saturated fat beverage with 3 oz. of peanuts, compared to a high-saturated

fat beverage with 42 g of an oil blend reflecting the fatty acid composition of the peanut beverage. In a similar study, it was shown that consuming peanuts with a high glycemic index (GI) meal improved 60-minute blood glucose response by 60% compared to the control in healthy subjects. There is also evidence showing that the addition of peanuts to a meal improves blood glucose response to the subsequent meal. Reis *et al.* reported that adding 42.5 g (1.5oz) of peanuts or peanut butter to a breakfast meal improved second meal blood glucose levels in obese women. These studies suggest that peanuts or peanut butter have a favorable effect on postprandial glucose levels.

There is also a growing body of evidence showing that nut consumption improves longer term glycemic control and risk factors for cardiovascular disease. A meta-analysis of 12 randomized controlled trials, showed that tree nut consumption reduced fasting blood glucose in individuals with type 2 diabetes by 0.15 mmol/L after approximately 8 weeks. We recently updated this meta-analysis and included all studies examining the effect of tree nuts and peanuts in adults (*unpublished*). Overall, there were improvements in insulin resistance and fasting insulin with nut consumption. A trend towards improvements in fasting blood glucose with nut consumption was also observed. In this review, five randomized controlled trials were identified that assessed the effect of peanuts on blood glucose levels, and these studies were heterogeneous in design, however in all of the studies the timing of peanut consumption was not controlled. We hypothesize that nighttime consumption of peanuts will result in improvements in fasting glucose levels based on known physiology and research demonstrating the glycemic benefit of evening consumption of healthful snacks.

## 2.3 Study Rationale

Provide the scientific rationale for the research.

There has been limited investigation of the influence of peanuts on fasting blood glucose, however based on the effects of peanuts and peanut butter on other markers of diabetes control including post-prandial blood glucose and circulating insulin levels, there is biologic plausibility for this hypothesis. Many of the studies that have been conducted have included healthy populations, and these findings cannot be generalized to people with pre-diabetes due to the poor glycemic regulation present in pre-diabetes. In addition, not all of the studies done to date have included nutrition counseling on timing and serving sizes of nuts added to the diet. We hypothesize that consumption of peanuts in the evening (after dinner and before sleep) will have a greater impact on fasting glucose than consumption at other times of the day. This is because peanuts and peanut butter are rich in MUFA, which delay gastric emptying and promote a slow and sustained release of carbohydrate that may act to stabilize overnight blood glucose levels and reduce the spike in glucose levels seen in the early morning, which makes subsequent glucose control throughout the day challenging.

The proposed project will generate **high quality robust data** in a cohort with pre-diabetes for: 1) the effect of consuming one ounce of peanuts as an evening snack (after dinner and before sleep) on glycemic control and risk factors for cardiovascular disease, compared with an isocaloric high carbohydrate snack; 2) changes that occur in the profile of the gut bacterial community in response to peanut consumption compared with an isocaloric high carbohydrate snack; 3) the relationship between markers of glycemic control and shifts in the microbiota in response to peanut consumption to elucidate the role of the microbiome in glucose regulation.

## 3.0 Inclusion and Exclusion Criteria

Create a numbered list below in sections 3.1 and 3.2 of criteria subjects must meet to be eligible for study enrollment (e.g., age, gender, diagnosis, etc.). Indicate specifically whether you will include any of the following vulnerable populations: (You may not include members of these populations as subjects in your research unless you indicate this in your inclusion criteria.) Review the corresponding checklists to ensure that you have provided the necessary information.

- Adults unable to consent

- Review “CHECKLIST: Cognitively Impaired Adults (HRP-417)” to ensure that you have provided sufficient information. HRP-417 can be accessed by clicking the Library link in CATS IRB (<http://irb.psu.edu>).
- **Individuals who are not yet adults (infants, children, teenagers)**
  - If the research involves persons who have not attained the legal age for consent to treatments or procedures involved in the research (“children”), review the “CHECKLIST: Children (HRP-416)” to ensure that you have provided sufficient information. HRP-416 can be accessed by clicking the Library link in CATS IRB (<http://irb.psu.edu>).
- **Pregnant women**
  - Review “CHECKLIST: Pregnant Women (HRP-412)” to ensure that you have provided sufficient information. HRP-412 can be accessed by clicking the Library link in CATS IRB (<http://irb.psu.edu>).
- **Prisoners**
  - Review “CHECKLIST: Prisoners (HRP-415)” to ensure that you have provided sufficient information. HRP-415 can be accessed by clicking the Library link in CATS IRB (<http://irb.psu.edu>).
- **Neonates of uncertain viability or non-viable neonates**
  - Review “CHECKLIST: Neonates (HRP-413)” or “CHECKLIST: Neonates of Uncertain Viability (HRP-414)” to ensure that you have provided sufficient information. HRP-413 and HRP-414 can be accessed by clicking the Library link in CATS IRB (<http://irb.psu.edu>).

### 3.1 Inclusion Criteria

List the criteria that define who will be included in your study.

Participants will be non-smoking males and females aged 18 to 75 years with impaired fasting glucose at screening ( $\geq 100$  mg/dL). Participants will have a BMI  $\geq 20$  and  $\leq 40$  kg/m $^2$ .

### 3.2 Exclusion Criteria

List the criteria that define who will be excluded in your study.

We will not recruit participants who have chronic disease risk factors that are diagnostic of diabetes (fasting glucose  $> 126$  mg/dL) or hypertension (SBP  $> 160$  mm Hg or DBP  $> 100$  mm Hg). In addition, they will not be taking anti-hypertensive, lipid lowering or glucose lowering drugs. Individuals with established CVD, stroke, diabetes, liver, kidney, autoimmune diseases or inflammatory conditions such as gastrointestinal disorders or rheumatoid arthritis will not be eligible. Other exclusion criteria will include: use of supplements (psyllium, fish oil, soy lecithin, and phytoestrogens) and botanicals and not willing to cease for the duration of the study; women who are pregnant, lactating, planning to become pregnant or have given birth in the past year; weight loss of  $\geq 10\%$  of body weight within the 6 months prior to enrolling in the study; or smoking or use of any tobacco products in past 6 months. Participants with an allergy/intolerance/sensitivity to test foods will be excluded (i.e. peanuts, gluten, grain products, cheese). Individuals consuming  $> 14$  alcoholic drinks/week or not willing to avoid alcohol consumption for 48 hour prior to test visit will be ineligible for the study.

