## 7.0 Study Design and Procedures

### 7.1 Study Design

Describe and explain the study design.

A two-period randomized crossover trial will be conducted. Participants will be randomized to receive each treatment for 6 weeks followed by a minimum 4-week wash-out period. During the peanut treatment, participants will consume one ounce per day (28 g) of peanuts as an evening snack. The control treatments will be an isocaloric high carbohydrate snack (crackers + spread) consumed after the evening meal. The peanuts and control foods will be provided to the participants every two weeks during the treatment periods; these foods will be purchased from one of the local supermarkets. Participants will be given instructions about when to consume the foods.

Fasting blood glucose, fructosamine, insulin, weight, lipids and lipoproteins, central and peripheral blood pressure and arterial stiffness will be measured at the beginning and the end of each treatment period. Fecal samples will be provided at the beginning and the end of each treatment period for assessment of the microbiome. A 24-hour dietary recall will be completed at the beginning and end of each diet to determine how consuming the evening snack influences overall dietary intake (including calorie and macronutrient intake and overall diet quality).

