### 7.2.1 EXAMPLE: Visit 1 or Day 1 or Pre-test, etc. (format accordingly)

Provide a description as defined above and format accordingly.

Screening: The clinical visit will consist of filling out forms (informed consent, medical history, personal information); measuring height and weight so that BMI can be calculated; and measuring blood pressure to determine eligibility. If blood pressure is >140/90 mmHg at screening the individual will require written approval from their Primary Care Physician prior to enrolling the study. Women of child bearing potential will provide a urine sample for a pregnancy test. If after these measurements, it is determined that the subject is still eligible, a blood sample will be taken and a complete blood count, including liver and kidney function and a blood lipid panel will be performed (approximately 19 mls of blood or ~1.25 tablespoon will be taken). If the initial blood draw is unsuccessful it may need to be repeated, with permission from the participant. In addition, if a potential participant takes thyroid medicine they must provide a current (within 6 months) lab test. If they do not have one, an extra 3.5 ml (0.2 Tbsp) of blood will be taken to conduct a thyroid test. If all eligibility criteria are met, participants will be scheduled for their baseline measurements. Baseline visits typically occur within 1-2 weeks following the screening appointment.

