### 8.3 Statistical methods

Describe the statistical methods (or non-statistical methods of analysis) that will be employed.

The normality of the data will be tested before performing analyses, and transformations will be made if needed. Mixed effect models will be used to determine between-group changes over time and between group differences in mean values following the treatments. Treatment will be included as a fixed effect. Subject will be included as a random effect.

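### Supplement users may enrol if they stop, but the plan sets no stop date and no supplement-free interval before the first baseline, so their period-1 change can include supplement withdrawal

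*Combined protocol and SAP*

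**What the plan says.** All references are to the combined protocol and SAP.

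- **Eligibility (3.2).** The exclusion reads "use of supplements (psyllium, fish oil, soy lecithin, and phytoestrogens) and botanicals and not willing to cease for the duration of the study". It joins use to unwillingness to stop, so a willing user qualifies. The same section gives look-back windows for tobacco (6 months) and weight loss (6 months), and a 48-hour alcohol window before test visits. It gives none for supplements.
- **Timing (7.2.1).** "Baseline visits typically occur within 1-2 weeks following the screening appointment". This is a usual interval, with no minimum or maximum. No run-in is described.
- **Wash-out (7.1).** "Participants will be randomized to receive each treatment for 6 weeks followed by a minimum 4-week wash-out period".
- **Measurement (7.1).** Glucose, fructosamine, insulin, weight, lipids, blood pressure and arterial stiffness "will be measured at the beginning and the end of each treatment period". For stool: "Fecal samples will be provided at the beginning and the end of each treatment period for assessment of the microbiome".
- **Analysis (8.3).** The quantities to be compared are given as follows: "Mixed effect models will be used to determine between-group changes over time and between group differences in mean values following the treatments". On the model terms, the section says only this: "Treatment will be included as a fixed effect. Subject will be included as a random effect". No period, sequence or prior-supplement term is named.
- **Supplement records (7.2.2).** The daily form names test foods, medication and health. The dietary recall does cover supplements, but only for the previous day at the start and end of each period, so it would not show when someone stopped.

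**The concern.** Listing these products as an exclusion implies that the plan expects them to matter for its endpoints. It gives its own snacks at least 4 weeks to clear, but sets no interval for the products it bars. A former user's first blood and stool samples may therefore still reflect the supplement, while the samples at the end of period 1 reflect it much less. That person's period-1 change then mixes the study food with supplement withdrawal.

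Two analyses use start-to-end change and are exposed: the change-over-time comparison in 8.3, and any correlation of microbiota shifts with glucose change (the second hypothesis, and the statement of purpose in 2.1). The correlation is the more exposed. If stopping a fibre supplement moves stool bacteria and glucose in the same people at the same time, an association appears that has nothing to do with peanuts, and randomising the order of foods does not cancel it. The period-1 baseline samples cannot be retaken later.

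**Working it through.** **1. The plan's own figure.** Inputs from 8.2: difference 10 mg/dL, SD 23.4 mg/dL, 80% power, p<0.05 (two-sided assumed), 45 completers. Reading the SD as that of within-person differences, a paired t-test gives n = 45 with power 80.1%. The stated 45 reproduces.

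**2. Time off supplements.** Assume stopping at the screening visit.

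| Time point | Weeks off |
|---|---|
| First baseline | 1 to 2 |
| End of period 1 (+6) | 7 to 8 |
| Start of period 2 (+4 or more) | at least 11 to 12 |

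**3. Where recovery falls.** The speed of recovery is not in the documents. As an illustration, assume exponential recovery with half-life h of 1 to 4 weeks. The share falling inside a 6-week period that starts t weeks after stopping is 2^(-t/h) - 2^(-(t+6)/h).

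| Period starts at | h = 1 | h = 2 | h = 3 | h = 4 |
|---|---|---|---|---|
| Week 1 (period 1) | 49% | 62% | 60% | 54% |
| Week 2 (period 1) | 25% | 44% | 47% | 46% |
| Week 4 (period 1, with lead-in) | 6% | 22% | 30% | 32% |
| Week 11 (period 2) | 0% | 2% | 6% | 10% |

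Recovery falls mainly in period 1, with little in period 2. A 4-week lead-in reduces the period-1 share but does not remove it when recovery is slow.

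**4. Effect on the treatment contrast in change.** The share of users f and the drift D are not in the documents. Assume f = 10 to 30% and D = 3 to 10 mg/dL, in period 1 only.

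- Noise: the SD of differences becomes sqrt(23.4² + fD²). At the worst corner, sqrt(547.56 + 0.3 × 100) = 24.0. Power at n = 45 falls from 80.1% to 77.9%. At the mildest corner (f = 10%, D = 3) it is 80.0%.
- Unequal sequences with no period term: the shift is fD(n1 - n2)/n. For a 25:20 split this is 0.1 × 3 × 5/45 = 0.03 up to 0.3 × 10 × 5/45 = 0.33 mg/dL.
- Chance imbalance of users: 9 users among 45, split 6 v 3 between sequences of 22 and 23, shifts the contrast by (6/22 - 3/23)/2 = 0.071 of their drift. At D = 10 mg/dL that is 0.7 mg/dL, against a design difference of 10.

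**5. Effect on a change-based correlation in period 1.** Suppose bacterial and glucose changes are otherwise independent with unit variance, and a share f is shifted by a (bacteria) and b (glucose), in SDs of change. With v = f(1 - f), the induced correlation has size

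r = v·a·b / sqrt[(1 + v·a²)(1 + v·b²)].

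Its sign depends on the directions of the two shifts. For a glucose drift, the only effect of a food change on fasting glucose given in the documents is 0.15 mmol/L (2.2, tree nuts in type 2 diabetes), or 0.15 × 18 = 2.7 mg/dL. Using it for supplement withdrawal is an assumption. Take a = 1. The SD of glucose change is not given, so use 23.4 mg/dL as a proxy and 8 mg/dL as an assumed smaller value.

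| f | SD 23.4 (b = 0.115) | SD 8 (b = 0.338) |
|---|---|---|
| 20% | 0.02 | 0.05 |
| 30% | 0.02 | 0.06 |

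Example: f = 20%, SD 8 gives 0.16 × 1 × 0.338 / sqrt(1.16 × 1.018) = 0.05.

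Larger values need the same large drift in both measures (a = b = d): 0.04 (f = 20%, d = 0.5), 0.08 (10%, 1), 0.14 (20%, 1), 0.17 (30%, 1) and 0.32 (30%, 1.5). With 45 pairs, p<0.05 needs |r| of about 0.29. All these values are for period 1 alone, and pooling both periods dilutes them.

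**The case against.** The strongest reply is that the design already protects what matters most. Order is randomised, 8.3 also compares means after each treatment, and the primary endpoint is fasting glucose. This stands. A reader might infer that withdrawal drift will be reported as a peanut effect, but the documents do not support that: the drift falls on whichever food comes first, equally in expectation. A split of users at least as uneven as 6 v 3 has about a 46% chance, but that is ordinary randomisation. With 9 users only 5 v 4 and 4 v 5 are more even, and the consequence is 7% of an unknown drift.

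A reader might also infer spurious correlations of 0.14 to 0.32. These need drifts of 1 to 1.5 SD in both measures. On the 23.4 mg/dL proxy that is about 23 to 35 mg/dL of glucose, in people admitted at 100 to 126 mg/dL. Nothing in the documents supports drifts of that size, though the true SD of change may be smaller.

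The third aim in 1.1 relates microbiota shifts to glycaemic markers after each treatment. If that wording governs, the glucose side is an end value and exposure is lower. The hypothesis and 2.1 refer to glucose lowering or change, so the exposure depends on which is analysed.

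Finally, the stop date is unstated rather than fixed at screening. A telephone screen comes earlier (4.4), its question list is not in the documents, and the 1 to 2 weeks is only typical. Some users could be off for longer, but nothing requires it. Nor does anything show that 4 weeks suits each product; it is simply the plan's own standard for its foods.

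**Conclusion.** The gap is real and its consequence is modest. As written, a former user can reach the first baseline 1 to 2 weeks off a product that the plan itself treats as incompatible with participation, and any recovery then falls mainly in period 1.

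This is not a systematic bias in the peanut-versus-control contrast. It adds some noise to the change-over-time comparison and some confounding to change-based microbiome-glucose correlations, which randomised order does not cancel. With a small glucose drift the spurious period-1 correlation is about 0.02 to 0.06.

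The user share (which could be near zero), the drift sizes, the recovery speed and stopping at screening are all assumptions. The missing stop date and interval are not. The point is worth acting on because the remedy is cheap and the baseline cannot be repaired afterwards.

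**What to change.** - In 3.2 and 7.2.1, state when the listed supplements and botanicals must stop. Require a supplement-free interval before the period-1 baseline blood and stool samples of at least the plan's own 4-week wash-out, or justify a shorter one. Keep the 1 to 2 week schedule for non-users.
- Record prior use of listed products and the stop date for every participant.
- In 8.3, include period as a fixed effect. This absorbs the average drift in the treatment contrast. It does not remove differences between users and non-users, so it supplements the interval and does not replace it.

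**Cost.** Protocol wording and one recorded item, with no added visits or tests. Users start about 2 to 3 weeks later (4 weeks less the usual 1 to 2), and a few may be lost in the wait. Slow recovery is reduced rather than removed: in the illustration, 6 to 32% still falls in period 1, compared with 25 to 62% at 1 to 2 weeks.

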**Fecal collection:** At the beginning and end of each treatment period, participants will be asked to collect a stool sample (~50 g). They will be provided with a stool sample kit and detailed instructions for collection of a clean sample.

**Dietary intake:** The 24-hour recall will be administered through the Automated Self Administered 24-Hour (ASA24®) Dietary Assessment Tool. This is an online system where participants will provide information about all foods, beverages and supplements consumed during the previous day. No identifying information is uploaded to this system, participant ID numbers are used to identify the 24-hour records. Participants will have the option of completing the 24-hour recall at home or at the visit. This system generates food group and nutrient data from the 24- hour recalls. These data will be used for calculation of diet quality.

**Daily monitoring form:** Participants will complete daily monitoring forms regarding consumption of test foods, changes in medication or health during the study. When they pick up their tests food biweekly, they will be provided with the daily monitoring forms and asked to return the completed forms the next time they pick up food.

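### Section 3.2 does not restrict recent antibiotic use or probiotic supplements, although two of the trial's three aims rest on gut bacterial change

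*Combined protocol and SAP*

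**What the plan says.** Among its exclusions, section 3.2 lists "use of supplements (psyllium, fish oil, soy lecithin, and phytoestrogens) and botanicals and not willing to cease for the duration of the study". A user of these products may therefore enter by agreeing to stop. On medicines, the section says that "they will not be taking anti-hypertensive, lipid lowering or glucose lowering drugs". On disease, it says that people with "inflammatory conditions such as gastrointestinal disorders or rheumatoid arthritis will not be eligible". Antibiotics, probiotics and prebiotics are not mentioned in eligibility (3.1, 3.2), removal criteria (3.3.1), study procedures (7.1 to 7.3) or statistical methods (8.3).

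Section 1.1 gives three aims, and two of them use stool data. Aim 2 is "To assess changes in the profile of the gut bacterial community in response to the peanut treatment", compared with the control snack. Aim 3 is "To investigate the relationship between markers of glycemic control, after each treatment, and shifts in the microbiota". Section 1.3 lists the microbiome as a secondary endpoint; the primary endpoint in 1.2 is fasting plasma glucose. Section 7.1 sets the sampling: "Fecal samples will be provided at the beginning and the end of each treatment period for assessment of the microbiome". That makes four samples per completer, across two 6-week periods and a washout of at least 4 weeks.

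Two instruments touch on exposure, both in 7.2.2. The daily monitoring form records "changes in medication or health during the study". The ASA24 recall covers foods, drinks and supplements for the previous day. Section 8.3 specifies a mixed model with treatment fixed and subject random, and has no rule or covariate for exposed stool samples.

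**The concern.** The products that must be stopped do not include those that act most directly on gut bacteria. As written, the plan can enrol someone who has just finished an antibiotic course and analyse that person's baseline sample like any other. The same applies to a course taken in the washout, just before the second baseline.

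Each person contributes only two period changes, so one disturbed sample distorts one of them. The stakes differ by analysis. In the peanut-versus-control contrast, exposure unrelated to treatment adds variance. In the aim 3 correlation, and in the second hypothesis of section 1.1 that ties bacterial shifts to the size of glucose lowering, a handful of extreme shifts among about 45 people could create an association or hide one. Exposure that nobody asked about at the time is hard to reconstruct later.

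**Working it through.** **The plan's own figure.** Section 8.2 gives 80% power, significance level 0.05, a difference of 10 mg/dL, SD 23.4 mg/dL and 45 completers. I read the SD as that of the within-person difference and the test as two-sided.
- Normal approximation: ((1.960 + 0.842) × 23.4 / 10)² = 42.98, so 43.
- Paired t-test (noncentral t): n = 45, with power 80.06%.

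The 45 reproduces. It concerns fasting glucose only. No sample size or power is stated for the microbiome, so this point does not contradict any planned figure.

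**What each instrument can capture.**
- Daily form (7.2.2): handed out and returned at the biweekly food pick-up, and 7.1 ties food supply to the treatment periods. It is not shown to cover the time before the first baseline or the washout. It asks about changes, so steady use need not appear.
- ASA24 recall (7.2.2): done at the same four time points as the stool samples, so it can pick up probiotic supplements taken the previous day. It cannot pick up an earlier antibiotic course.
- Medical history form (7.2.1) and telephone screening form (4.4): they may ask, but the questions were not supplied, and no section says how an answer would be used.

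**Size, under assumptions.** The documents give neither an exposure rate nor a microbiome variance. Assume that a share f of participants is exposed and that their within-person differences have v times the usual variance, with the mean treatment effect unchanged.
- Variance inflation = 1 + f(v − 1); effective n = 45 / inflation.
- f = 5%, v = 2: 1 + 0.05 × 1 = 1.05; 45 / 1.05 = 42.9.
- f = 5%, v = 4: 1 + 0.05 × 3 = 1.15; 45 / 1.15 = 39.1.
- f = 15%, v = 2: 1 + 0.15 × 1 = 1.15; 45 / 1.15 = 39.1.
- f = 15%, v = 4: 1 + 0.15 × 3 = 1.45; 45 / 1.45 = 31.0.

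The range is about 43 down to 31.

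**The same in power.** Take a microbiome summary measure that would have exactly 80% power at n = 45 (standardised paired difference 0.427). With v from 2 to 4, power falls to 78%-74% at f = 5% and to 76%-69% at f = 10%. Completers needed to restore 80% rise to 48-52 and 50-58.

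**The case against.** The strongest reply is that the plan already has partial controls, and that the consequence is limited to imprecision in a secondary endpoint. Much of that stands. Gastrointestinal disorders are excluded, and the recall samples current supplement use at every stool time point. The telephone screen covers dietary habits, medical history and lifestyle (5.2.2), and its full question list is not available here. Steady probiotic use in both periods is partly removed by the within-person comparison. What remains is mainly antibiotic courses before the first baseline or in the washout, and the absence of any rule for using whatever is recorded.

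A reader might infer that every microbiome comparison is compromised. The documents do not support that. Noise enters only if someone is exposed. One of the two contrasts in 8.3, the comparison of values after each treatment, does not use the baseline samples, so a course before a baseline chiefly affects the change-from-baseline comparison.

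A reader might also infer a much larger loss. If exposed samples moved by 2-3 SDs of the within-person difference in 5-15% of people, inflation would be 1 + f × k², from 1 + 0.05 × 4 = 1.20 to 1 + 0.15 × 9 = 2.35, and effective n would run from 37.5 down to 19.1. That implies a mean squared difference 5 to 10 times the usual (1 + k²) in exposed participants. Nothing in the documents supports shifts of that size.

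Finally, removing samples taken after randomisation from the main analysis would sit awkwardly with the intent-to-treat wording in 3.3.2. That objection stands and shapes the fix.

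**Conclusion.** The omission is real and worth correcting. Section 3.2 restricts neither recent antibiotic use nor probiotics, and the supplied text does not show that exposure before the first baseline or in the washout would be known. With randomised sequence, and provided exposure is unrelated to treatment, the microbiome contrasts lose precision and are not biased. The glucose-microbiome correlation is more fragile, because a few outlying shifts can dominate it. The illustrative loss, from 45 to between about 43 and 31 effective completers, rests wholly on the assumed 5-15% exposure and 2-4 times variance. The finding does not touch fasting glucose, its 45 completers or the other non-stool endpoints. It is a cheap improvement to two secondary aims. The telephone screening form could narrow the gap if it already asks about these products, but a rule for acting on the answers would still be needed.

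**What to change.** - **Section 3.2:** make recent antibiotic use, over a period the investigator sets, a reason to defer the baseline visit of either period. Add probiotics to the supplements to be stopped, or held constant, for the study.
- **Sections 4.4 and 7.2:** ask about antibiotic and probiotic use at screening and at each of the four stool collections, so that the washout is covered. The daily form alone is not enough for this.
- **Section 8.3:** pre-specify a sensitivity analysis of the microbiome endpoints and the glucose-microbiome correlation without exposed samples. Keep all participants in the glucose and other analyses.

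The cost is a few deferred visits, one extra question per stool collection and a short addition to the analysis text. There is one downside to weigh. Baseline visits typically follow screening by 1-2 weeks (7.2.1) and no run-in is described, so participants who stop probiotics shortly before baseline may drift early in period 1. Holding use constant avoids that. The change is best made before enrolment, because past exposure is hard to recover afterwards.
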